### **3. INTRODUCTION**

As per International Conference on Harmonisation E9 (ICH E9) the purpose of this document is to provide a more technical and detailed elaboration of the principal features of the analysis described in the protocol, and to include detailed procedures for executing the statistical analysis of the primary and secondary variables and other data.

This Trial Statistical Analysis Plan (TSAP) assumes familiarity with the Clinical Trial Protocol (CTP), including Protocol Amendments. In particular, the TSAP is based on the planned analysis specification as written in CTP Section 7 “Statistical Methods and Determination of Sample Size”. Therefore, TSAP readers may consult the CTP for more background information on the study, e.g. on study objectives, study design and population, treatments and definition of measurements and variables.

The study was initially planned to be a single arm, open label trial consisting of two parts: a Phase Ib dose escalation part and a Phase II part investigating one expansion cohort. Approximately 60 chronic lymphocytic leukaemia (CLL) patients who qualify for treatment with ibrutinib were to be treated with a combination of BI 836826 and ibrutinib in this trial. Approximately 20 patients were intended to be enrolled in Phase Ib and 40 patients were intended to be enrolled in the Phase II part of this study.

Dose-escalation of BI 836826 is guided by a Bayesian Logistic Regression Model (BLRM) with overdose control. The BLRM estimates the maximum tolerated dose (MTD) by updating estimates of the probability of observing a dose limiting toxicity (DLT) in the MTD evaluation period for each dose level in the study as patient information becomes available. At any time in the trial, it is not permitted to escalate to a dose which does not fulfil the escalation with overdose control (EWOC) criterion. Dose-increments are  $\leq 100\%$  of the previous dose level tested in the previous cohort.

Due to the strategical decision to stop the project, the Phase II part of the trial will not be conducted. Therefore, this TSAP only describes the analysis of the Phase Ib part of the trial, based on CTP amendment 1 which reflects this change in the study set-up. The decision was made that an abbreviated clinical trial report (CTR) will be written for this trial instead of a full CTR. Therefore, only analyses mandatory to be reported and additional analyses deemed necessary by the trial are described in this TSAP and will be included in the abbreviated CTR.

In the following, study medication always refers to either BI 836826 or ibrutinib.

SAS® Version 9.4 or higher will be used for all analyses.

#### **4. CHANGES IN THE PLANNED ANALYSIS OF THE STUDY**

**Clarifications:**

**Changes:**

## **5. ENDPOINTS**

### **5.1 PRIMARY ENDPOINTS**

The primary endpoints of the trial are:

- Recommended Phase II dose (RP2D) of BI 836826 in combination with ibrutinib. If a MTD can be determined based on the criteria as described in Section 7 of the CTP, the RP2D will be either the MTD or a lower dose. The RP2D will be determined by the safety review committee (SRC) based on safety and efficacy considerations.
- Number of patients with DLTs during the MTD evaluation period (starting at the day of first administration of BI 836826, lasting until 14 days after the Day 15 administration of BI 836826 in the first cycle)

For definition of DLT, refer to CTP Section 5.3.6.2.

### **5.2 SECONDARY ENDPOINTS**

#### **5.2.1 Key secondary endpoints**

Not applicable.

#### **5.2.2 Other secondary endpoints**

The secondary endpoint is the MTD. The MTD may be considered reached if the posterior probability that the true DLT rate is in the target interval  $[0.16, 0.33)$  is larger than 0.5 or if at least 15 patients have been treated in the Phase Ib part, of which at least 6 at the MTD. Patients who have been replaced are not considered evaluable for MTD determination. Only DLTs occurring in the MTD evaluation period will be considered for the determination of the MTD

## 6. GENERAL ANALYSIS DEFINITIONS

### 6.1 TREATMENTS

In this trial, treatments are not randomized (open-label, dose-escalation). Different dose levels of BI 836826 in combination with ibrutinib are being administered. All planned analyses will be presented by initial treatment group, i.e. for all dose cohorts separately and in total over all dose cohorts.

To justify the RP2D / MTD determination, DLTs occurring during the MTD evaluation period will be presented separately from those occurring during the whole on-treatment period. Patients where treatment group assignment has not been followed will be handled on a case-by-case basis and will be agreed upon latest at the report planning meeting before database lock.

For safety summaries events that start from first administration of BI 836826 and last until 30 days (residual effect period (REP)) after the last administration of BI 836826 will be considered as having occurred “on treatment”. If not specified otherwise, all safety tables will be based on the on-treatment period. AEs that have an onset date during the screening, run-in, or post-study period will be displayed in separate listings from those occurred during the on-treatment period (refer to [Section 7.8.1.2](#) for details).

Labels of each analysis treatment period, analysis numbers, the labels used for displays in the tables and listings in the CTR, as well as codes, decodes, sort order and labels for each trial medication are provided in the TSAP technical document analysis dataset (ADS) plan.

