7.3.4 Safety analyses

Adverse events will be coded using the Medical Dictionary for Regulatory Activities (MedDRA) coding dictionary. Standard BI summary tables and listings will be produced. All AEs with an onset between start of treatment with BI 836826 and end of the REP, a period of 30 days after the last dose of BI 836826, will be assigned to the treatment period for evaluation. All treated patients will be included in the safety analysis. In general, safety analyses will be descriptive in nature and will be based on BI standards. No hypothesis testing is planned.

Statistical analysis and reporting of AEs will concentrate on treatment-emergent AEs. To this end, all AEs occurring between start of treatment with BI 836826 and end of the REP will be considered 'treatment-emergent'. The REP is defined as last administration of BI 836826 plus 30 days. Adverse events that start before first intake of BI 836826 and deteriorate under treatment will also be considered as 'treatment-emergent'. Adverse events occurring during screening and/or run-in period with ibrutinib as well as during post-treatment will be listed separately.

Analyses of AEs of all treatment cycles will be carried out under the initial treatment.

Adverse events will be graded according to CTCAE Version 4 and reported according to BI standards.

Serious Adverse Events, drug-related AEs and AESI will be tabulated. In addition, events leading to treatment discontinuation will be examined.

Frequency, severity, and causal relationship of AEs will be tabulated by system organ class and preferred term after coding according to the current version of the MedDRA.

Descriptive statistics will be used to describe changes in laboratory tests over time. In addition, all abnormalities of potential clinical significance will be reported. In general, potential clinical significance is defined as at least CTC Grade 2 and an increase in CTC

classification from baseline. Hematologic toxicity based on laboratory values will be not only described using CTCAE grading but also using the criteria described in the ‘Guidelines for the diagnosis and Treatment of CLL ([R10-4429](#)).

Vital signs, physical examinations, or other safety-relevant data observed at screening, baseline, during the course of the trial and at the end-of-trial evaluation will be assessed with regard to possible changes compared to findings before start of treatment.

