#### **7.8.1.2 Adverse events**

Unless otherwise specified, adverse events analyses will be performed for the on-treatment period. Selected analyses will be repeated for the MTD evaluation period and for the run-in period.

The analyses of AEs will be descriptive in nature and will follow the standard procedure laid down in (4). All analyses of AEs will be based on the number of patients with AEs and NOT on the number of AEs.

AEs will be coded with the most recent version of MedDRA. The version number will be displayed as a footnote in the respective tables and listings. The severity of AEs will be scaled according to CTCAE version 4.0.

The system organ classes (SOCs) will be sorted alphabetically. In tables displaying AEs by dose cohort, preferred terms (PTs) will be sorted by descending frequency of adverse events in the “Total” BI 836826 group.

Each patient can be observed during the trial under several doses. Analysing the AEs of all treatment courses will be carried out under the initial treatment. No formal statistical analysis is planned for the safety comparison.

The analysis of AEs will be based on the concept of treatment emergent AEs. That means that all AEs occurring from the first administration of BI 836826 until 30 days after last administration of BI 836826 will be assigned to the on-treatment period. All AEs occurring before first administration of any trial medication will be assigned to “Screening”, all AEs occurring after the first administration of ibrutinib and before the first administration of BI 836826 will be assigned to “Run-in” and all AEs occurring after last administration of BI 836826 + 30 days will be assigned to “Post-study” (for listings only). The actual planned dosage of BI 836826 and ibrutinib administered on the day each AE starts will also be derived and will be included in the listing. Listings of screening events will not be sorted by initial treatment. Post-study listings will be sorted by initial treatment. For details on the treatment definition please refer to [Section 6.1](#).

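### The SAP's on-treatment definition drops the protocol rule that adverse events starting before BI 836826 and worsening under it count as treatment-emergent

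*SAP*

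**What the plan says.** Protocol 7.3.4 builds the treatment-emergent set in two parts. The first is AEs occurring between the start of BI 836826 and 30 days after its last administration. The second extends it: "Adverse events that start before first intake of BI 836826 and deteriorate under treatment will also be considered" treatment-emergent. The same section also says that screening and run-in AEs are listed separately.

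SAP 6.1 classifies by start of the event. On-treatment covers "events that start from first administration of BI 836826 and last until 30 days" after the last administration, and "AEs that have an onset date during the screening, run-in, or post-study period will be displayed in separate listings".

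SAP 7.8.1.2 says the AE analysis rests on the treatment-emergent concept and then explains it: "That means that all AEs occurring from the first administration of BI 836826 until 30 days after last administration of BI 836826" go to the on-treatment period. AEs before any trial medication go to Screening, and "all AEs occurring after the first administration of ibrutinib and before the first administration of BI 836826 will be assigned to" Run-in. No exception is made for later worsening. The section closes the loop with "For details on the treatment definition please refer to" Section 6.1, and 6.1 in turn points to 7.8.1.2.

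SAP section 3 states that "the TSAP is based on the planned analysis specification as written in CTP Section 7", which includes 7.3.4.

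**The concern.** Every patient takes ibrutinib alone for about two weeks before the first BI 836826 infusion. An event that begins in that run-in and becomes more severe when the antibody is added bears directly on the safety of the combination, and the protocol's second clause is there to keep it in the count.

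Under the SAP's dates, such an event, if held as a single record with its original start date, belongs to Run-in. It would then be absent from the on-treatment tables: drug-related AEs, serious AEs, AEs leading to discontinuation or dose reduction, and AEs of special interest. Those tables would understate what patients experienced on the combination, and they would not be the tables the protocol describes. The point concerns mainly non-laboratory events, because laboratory worsening is shown elsewhere.

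**Working it through.** **Step 1: compare the rules.** The documents give no figure to reproduce, so the check begins with the text. Three cases, assuming BI 836826 is ongoing:

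| AE | Protocol 7.3.4 | SAP 6.1 and 7.8.1.2 |
|---|---|---|
| Starts after first BI 836826 | Treatment-emergent | On-treatment |
| Starts in run-in, does not worsen | Listed separately | Run-in |
| Starts in run-in, worsens after BI 836826, one record | Treatment-emergent | Run-in |

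The start of the window and its 30-day tail agree. The documents differ only in the third row. If the worsening is entered as a new record dated after first BI 836826, it falls in the first row and there is no difference.

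**Step 2: how many events could be affected?** The documents give no rate of run-in AEs that later worsen, so this is an illustration.

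*Inputs from Protocol 1.2.2:* six common non-hematologic reactions to ibrutinib over a median exposure of 8.6 months: diarrhea 48%, nausea 26%, fatigue 28%, pyrexia 24%, rash 24%, musculoskeletal pain 28%. *Input from the flow chart:* a 14-day run-in.

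*Lower case, constant hazard (assumption), with the median taken as common exposure.*
- 8.6 × 365.25/12 = 261.8 days; 14/261.8 = 0.0535.
- Run-in risk = 1 − (1 − p)^0.0535: diarrhea 3.4%, nausea 1.6%, fatigue 1.7%, pyrexia 1.5%, rash 1.5%, musculoskeletal pain 1.7%.
- Sum, from unrounded values: 0.114 onsets per patient, which gives 2.29 in 20 patients and 1.14 in 10.

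*Upper case, 25% of all onsets fall in the run-in (assumption).*
- Sum of p = 0.48 + 0.26 + 0.28 + 0.24 + 0.24 + 0.28 = 1.78.
- 1.78 × 0.25 = 0.445 per patient, which gives 8.9 in 20 and 4.45 in 10.

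*Share that later worsens: 5% to 30% (assumption).*
- n = 20: 2.29 × 0.05 = 0.11 to 8.9 × 0.30 = 2.67 patient-by-term rows.
- n = 10: 1.14 × 0.05 = 0.06 to 4.45 × 0.30 = 1.34.

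Screening AEs and other terms are not included.

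**Step 3: how far can one patient move a row?** At most 1/20 = 5.0 percentage points overall, 1/15 = 6.7 or 1/10 = 10.0; within a cohort, 1/6 = 16.7 or 1/3 = 33.3. Totals of 15 and 10 are assumptions, included because recruitment was stopped; Protocol 3.1 sets cohorts of at least three. The shift is zero if the patient already has an on-treatment event of the same or higher grade in that row.

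**The case against.** - **The protocol itself supports the SAP's wording.** 7.3.4 also assigns AEs to the treatment period by onset and lists run-in AEs separately, and 5.3.7 uses the term on-treatment without a deterioration clause. This is true, and the protocol could say more plainly how one event can be both listed and counted. But its deterioration sentence is an explicit addition to the onset rule, and the SAP's explanation of treatment-emergence leaves it out.
- **The rule may sit in text not available for review.** The content of SAP sections 4 and 5.4, the analysis dataset plan and the internal AE standard cannot be seen. This stands as a limit: a rule there cannot be excluded. Even so, the two definitions that can be read would classify the event differently from the protocol.
- **The loss depends on how worsening is recorded.** Protocol 5.3.7 requires worsening of pre-existing conditions to be recorded as an AE, and SAP 7.8.1.2 uses CTCAE grade when collapsing records. Neither settles what happens to an AE that began in the run-in: the first does not expressly cover it, and the second acts on records already present without saying that a single record is split. Where a new record is made, the point has no effect.
- **The information is not lost.** Run-in AEs are listed with grade, "Selected analyses will be repeated for the MTD evaluation period and for the run-in period", and SAP 7.8.2 tabulates changes in laboratory grade from baseline. This stands and reduces the consequence. A listing is still not the count the protocol specifies, and non-laboratory events have no such transition table.
- **Little depends on the result.** Development has ended, the report is abbreviated and the tables are descriptive. This limits the weight of the point, not its correctness.

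**Conclusion.** The concern holds. As visible, the SAP states a rule that gives a different answer from Protocol 7.3.4 for AEs that begin before BI 836826 and worsen under it, and no departure is declared in the text available.

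The expected effect is small: about 0.1 to 2.7 patient-by-term rows among 20 patients, or 0.06 to 1.3 among 10, and possibly none. That range rests on three things the documents do not give: the timing of onsets, the 5% to 30% share that worsens, and worsening being kept in a single record. The direction is not in doubt, since any effect lowers the reported on-treatment frequencies. The alignment should be made, but the point is confined to descriptive AE tables and gives no reason to question the DLT count, MTD or RP2D. Confidence is medium because of the text that could not be seen.

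**What to change.** Add the deterioration clause of Protocol 7.3.4 to SAP 6.1 and 7.8.1.2, and keep the run-in listing. Because the protocol does not define deterioration, the SAP should state its criterion. One workable version: an increase in CTCAE grade between the first BI 836826 administration and 30 days after the last, with the event counted at its on-treatment grade. If the omission is intended, or the rule already sits in another document, SAP section 4 should declare the former and 7.8.1.2 should cite the latter.

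The cost is two sentences and one derivation in the AE dataset, with no new assessments. A few AEs held as one record may need manual review to date the worsening. Reported on-treatment AE rates would be slightly higher.

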### 6.2 IMPORTANT PROTOCOL VIOLATIONS

No per protocol set analysis will be performed for this study, hence no patient will be excluded from the analyses. However, patients with important protocol violations (IPVs) will be documented. The following table defines the different categories of IPVs.

Table 6.2 : 1 Important protocol violations

| Category / Code   | Description   | Example/Comment  | Excluded from |
|-------------------|---|--|---------------|
| A          | Entrance criteria not met  |  |               |
| A1 a   | Patient has condition that may cause additional risk from study medication    | Check Inclusion/Exclusion criteria:
In6, In8
Ex4, Ex9, Ex10, Ex11, Ex12, Ex13, Ex16,
Ex17, Ex18, Ex19 | None          |
| A2 a   | Patient has laboratory assessments that may cause additional risk             | Check whether baseline laboratory data comply with thresholds as defined by In7 and check that In7 = “Yes”     | None          |
| A3 a   | Patient is unable to comply with the protocol                                 | Check Ex20   | None          |
| A4 a+m | Patient does not have trial diagnosis or is not part of the target population | Check Inclusion/Exclusion criteria:
In1, In2, In3, In4, In9, In10
Ex1, Ex3, Ex5, Ex6, Ex7                | None          |
| B          | Informed consent   |  |               |

Table 6.2 : 1 Important protocol violations (cont.)

|          |                   |   |  |      |
|----------|-------------------|---|--|------|
|          | B1 a   | Informed consent not given or too late                | Check In12
Check date of IC against date of Screening visit   | All  |
| C |                   | Trial medication and randomisation             |  |      |
|          | C1 a+m | Drug not administered according to protocol           | Infusion schedule followed = “No” and medical review of associated comments  | None |
|          | C2 a   | Drug administration not according to schedule         | Ibrutinib not administered continuously from start of Run-in period
Cycle 1: pre-dose of 10 mg of BI836826 not administered on Day 1 and 50% of target dose on Day2 and Day 8 and 100% of target dose on Day 15.
Cycles 2-4: 100% of target dose of BI836826 not administered on days 1 and 15 of each cycle
Cycles 5-24: 100% of target dose of BI836826 not administered on day 1 of each cycle | None |
|          | C3 a   | Incorrect treatment taken                             | Study drugs dispensing error leading to change in actual treatment   | None |
| D |                   | Concomitant medication                         |  |      |
|          | D1 a+m | Prohibited medication                                 | 
 
• anti-neoplastic therapy
 
• long-term use (>7 days)of strong CYP3A inhibitor (check also Ex15)
 
• Oral anti-coagulants (check also Ex14)
 
 ongoing systemic immunosuppressive therapy other than corticosteroids (check also Ex8)  | None |
|          | D2 a+m | Pre-medication not administered according to protocol | Did the subject receive standard pre-medication = “No” to any standard pre-medication and medical review of associated comments – only until cycle 6, afterwards pre-medication according to investigator judgement  | None |

a = automated IPV; m = manual IPV; In = Inclusion criterion; Ex = Exclusion criterion

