4.2.1.2.1 Pre-Medication prior to BI 836826 infusion

Pre-medication is mandatory 30-120 minutes prior to the administration of BI 836826 to mitigate the risk for IRRs. In case a contra-indication for one of the drug exists, the drug may be replaced or omitted. If BI 836826 has been well tolerated without signs of IRRs during cycle 2, the glucocorticoid dose may be reduced in Cycle 3 while the other drugs are maintained. The first step in cycle 3 may be a reduction from 100 mg to 50 mg prednisolone or equivalent. If the cycle 3 doses are tolerated without IRR, the glucocorticoid may be reduced to 25 mg prednisolone or equivalent prior to a subsequent administration in cycle 4. If BI 836826 is tolerated without IRR after pre-medication with prednisolone 25 mg or equivalent, acetaminophen and antihistamine in cycle 4, the investigator may individually decide whether to administer pre-medication in cycle 5 and subsequent treatment cycles and which of the recommended drugs to use.

All pre-medications with doses should be source documented.

If IRRs are still seen at later infusions, pre-medication triplet should continue to be used for all administrations.

Table 4.2.1.2.1:1 Premedication table

Cycle	Patients Requiring Premedication	Premedication	Completion Prior to BI 836826
1-2	all patients	Analgesic/Antipyretic p.o. or i.v. ¹ Antihistamine p.o. or i.v. ² Glucocorticoid i.v., equivalent to prednisolone 100 mg	60-120 minutes
3	all patients with IRR in the previous infusion and/or with ALC $\geq 25000/\mu\text{l}$	Analgesic/Antipyretic p.o. or i.v. ¹ Antihistamine p.o. or i.v. ² Glucocorticoid i.v., equivalent to prednisolone 100 mg	60-120 minutes
3	patients without IRR in previous infusion and ALC $< 25000/\mu\text{l}$	Premedication Level -1: Analgesic/Antipyretic p.o. or i.v. ¹ Antihistamine p.o. or i.v. ² Glucocorticoid i.v., equivalent to prednisolone 50 mg	30-120 minutes
4 and subsequent Cycles	patients with ALC $< 25000/\mu\text{l}$ and without IRR and premedication at level -1 at previous infusion	Premedication Level -2: Analgesic/Antipyretic p.o. or i.v. ¹ Antihistamine p.o. or i.v. ² Glucocorticoid i.v., equivalent to prednisolone 25 mg	30-120 minutes
5 and subsequent Cycles	patients with ALC $< 25000/\mu\text{l}$ and without IRR and premedication at level -2 at previous infusion	Premedication at the discretion of the investigator	

¹ equivalent to Acetaminophen/Paracetamol; ²1000 mg equivalent to diphenhydramine 50 mg i.v.

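### The SAP's table of important protocol violations can miscount premedication and eligibility breaches, and its consent row contradicts the no-exclusion statement

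*SAP*

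**What the plan says.** **Premedication (item D2).** SAP Table 6.2:1 takes a 'No' to any standard premedication drug as the trigger, "and medical review of associated comments", and limits the check: "only until cycle 6, afterwards pre-medication according to investigator judgement". The item is marked as both automated and manual.

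Protocol 4.2.1.2.1 has a conditional rule. If the reduced regimen was tolerated in Cycle 4 without an IRR, "the investigator may individually decide whether to administer pre-medication in cycle 5 and subsequent treatment cycles". The premedication table in that section restricts this to patients with ALC below 25000/µl "without IRR and premedication at level -2 at previous infusion". The section also states: "If IRRs are still seen at later infusions, pre-medication triplet should continue to be used for all administrations". It lets a contra-indicated drug be replaced or left out, with no limit by cycle.

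**Eligibility (items A1 to A4, B1, D1).** Each row names the criteria to check. For example, A4 names the inclusion criteria "In1, In2, In3, In4, In9, In10".

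**Consent (item B1).** The text above the table says there is no per-protocol set, "hence no patient will be excluded from the analyses". In the column stating what a patient is excluded from, B1 (consent missing or too late) has the entry All. Every other row has None.

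The number of patients with important violations is a planned display (SAP 7.1.2).

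**The concern.** D2 is meant to record departures from the protocol's premedication rule, but its window matches that rule in neither direction. It opens permitted omissions to flagging in Cycle 5, and in Cycle 6 if 'until' is inclusive. It then stops looking, even for patients in whom the protocol says the triplet should continue.

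The eligibility rows leave gaps with no stated reason. In5 sets the washout from prior CLL treatment, Ex2 concerns recent allogeneic transplant or active graft-versus-host disease, and Ex21 concerns taking part in another therapeutic trial. These bear on safety and on the target population as much as the criteria that are listed.

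B1 and the sentence above the table give opposite instructions for the same patient. This is the part that could reach beyond a descriptive count. The Treated Set carries the safety analyses and the MTD evaluation set carries the primary DLT table, and SAP 6.3 defines both without mentioning consent.

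**Working it through.** No power or error-rate calculation is involved. The check is a comparison of passages and two counts.

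**Step 1. Size of the D2 mismatch.** Scheduled BI 836826 infusions (protocol 4.1.1): 4 in Cycle 1, 2 in each of Cycles 2 to 4, and 1 per cycle from Cycle 5.

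- Cycles 1-12: 4 + 3 × 2 + 8 × 1 = 18, which reproduces the 18 infusions in the synopsis.

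| Reading of 'until cycle 6' | Checked although discretion is possible | Not checked, to Cycle 12 | Not checked, to Cycle 24 |
|---|---|---|---|
| Cycle 6 inside the window | Cycles 5-6: 2 infusions | Cycles 7-12: 6 | Cycles 7-24: 18 |
| Cycle 6 outside the window | Cycle 5: 1 infusion | Cycles 6-12: 7 | Cycles 6-24: 19 |

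These are the most infusions per patient at which D2 and the protocol can disagree. They are not expected numbers of errors. The left-hand count applies only to a patient who meets all the conditions for discretion and from whom a drug was actually withheld. The right-hand counts apply only where the protocol still calls for premedication and it was not given.

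**Step 2. Eligibility coverage.** The protocol has 12 inclusion and 21 exclusion criteria, 33 in all.

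| Row | Inclusion | Exclusion |
|---|---|---|
| A1 | 6, 8 | 4, 9, 10, 11, 12, 13, 16, 17, 18, 19 |
| A2 | 7 | none |
| A3 | none | 20 |
| A4 | 1, 2, 3, 4, 9, 10 | 1, 3, 5, 6, 7 |
| B1 | 12 | none |
| D1 | none | 8, 14, 15 |
| Total | 2 + 1 + 6 + 1 = 10 of 12 | 10 + 1 + 5 + 3 = 19 of 21 |

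Covered: 10 + 19 = 29 of 33. Absent: In5, In11, Ex2 and Ex21, so 4/33 = 12%.

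**Step 3. Cover elsewhere for the four.**

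- In5: previous therapies are tabulated (SAP 7.1.3) and D1 covers anti-neoplastic therapy. Neither tests the intervals of 1 week, 48 hours and 4 weeks before ibrutinib.
- Ex2: previous transplants are tabulated (SAP 7.1.3), but no row checks the one-year limit. Active graft-versus-host disease might surface through Ex8 or Ex17.
- Ex21: D1 would catch an anti-neoplastic drug from another trial, but not other trial treatments.
- In11 (ibrutinib sourcing): protocol 6.2.1 makes anyone with under 80% of run-in ibrutinib doses a screen failure. A patient who goes on to BI 836826 under that rule has therefore obtained the drug.

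**Step 4. B1 against SAP 6.3.** The Treated Set is everyone given BI 836826 at least once. The MTD evaluation set is the same group less replaced patients. Under those definitions and the text of 6.2, a treated patient who consented late is in both sets; under B1 the patient is in no analysis. With about 20 patients planned, one such case is 1/20 = 5% of the Treated Set, and a larger share if fewer were treated.

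**The case against.** The strongest reply is that nothing here shows a wrong result. D2 does not count a 'No' by itself, because medical review comes first, and its title ties it to the protocol. The cycle limit sits in a column for examples and comments. Later omissions are not hidden either: SAP 7.3 plans a listing of every BI 836826 administration with its premedication, without a cycle limit. The table is for important violations, so some selection among criteria is expected. The sentence that nobody is excluded follows from the absence of a per-protocol set, and B1 may be meant as the obvious exception.

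Much of this stands, and it rules out several stronger readings that a reader might infer:

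- **That D2 misclassifies one or two cycles for each patient who tolerates Cycle 4.** Permission to omit is not omission, and tolerance alone does not confer discretion. ALC and premedication level at the previous infusion also count, and medical review can clear the record.
- **That washout, transplant or concurrent-trial breaches would never be seen.** Baseline tables and D1 give partial cover.
- **That DLT attribution is compromised.** Investigators judge DLTs from drug-related events (protocol 5.3.6.2). The violation table does not feed that judgement or the model.

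Three things survive. Medical review of flagged records has no written clearing rule and cannot recover what is never flagged after Cycle 6. A listing is not the planned count. For consent, a table entry that contradicts the sentence above it leaves the programmer to choose.

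**Conclusion.** The point holds as a defect of specification with limited reach. As written, the table can overcount premedication violations around Cycles 5 and 6, cannot count them later, omits three relevant eligibility criteria and one of little consequence, and gives contradictory instructions on late consent. Whether any count is actually wrong depends on such events occurring, which the documents do not show.

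The size is one descriptive count in an abbreviated report and, through B1, possibly one patient's place in the Treated and MTD evaluation sets. The 5% figure assumes one case among about 20 treated patients. The DLT definition and the Bayesian logistic regression model are unaffected. Correction is worthwhile because it is cheap, and because this count was kept when the report was abbreviated.

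**What to change.** 1. **D2.** Define it as departure, at any cycle, from the protocol's conditional premedication rule. Keep the medical review and write in the contra-indication exception. The protocol passages need reconciling first: 4.1.4.1 calls premedication required before each administration, then says it should be considered from Cycle 2 Day 1, while 4.2.1.2.1 sets out the stepwise rule. Which clinical rule applies is for the sponsor to settle. D2 should refer to that rule and not carry its own cut-off; a fixed cycle applied to all patients would also flag omissions that the contra-indication clause permits.
2. **Eligibility.** Add In5, Ex2 and Ex21 to A1 or A4. Add In11, or say why it is left out.
3. **B1.** Make the B1 entry, the no-exclusion sentence in SAP 6.2 and the set definitions in SAP 6.3 agree, with explicit wording for treated patients whose consent was late.

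The cost is a few cells in one SAP table, a sentence in 6.2 or 6.3, and the matching change to the automated checks. No new data are called for.
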